## 4.6 Analysis of Safety

### 4.6.1 Adverse Events and Serious Adverse Events

All adverse events (AEs) will be summarised by primary system organ class and preferred term according to the current version of the MedDRA.

Treatment emergent adverse events (TEAEs) will be summarized by the number and percentage of subjects having any adverse event, an adverse event in each System Organ Class, and each individual adverse event ([Table 14.3.1.1](#)). All TEAEs will also be tabulated by severity ([Table 14.3.1.2](#)). Treatment-emergent AEs suspected of a relationship to study product will be presented in a similar manner ([Table 14.3.1.3](#)). For treatment-related AEs, these will also be presented by severity ([Table 14.3.1.4](#)).

Deaths occurring during treatment (if any) will be listed ([Listing 14.3.2.1](#)) by treatment, including the date and study day of death, and the principal cause of death. Serious adverse events leading to discontinuation will be listed ([Listing 14.3.2.2](#)).

All AEs will be listed in the [Listing 16.2.7.1](#) and [Listing 16.2.7.2](#).

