For the primary endpoints, individual observations will be assessed based on Appendix 3 and Appendix 4 and a narrative description of all cutaneous and ocular responses will be provided. A frequency tabulation of the number of subjects with any cutaneous and ocular response versus those without any cutaneous and ocular response for each assessment will be presented at each time point for each of the test products. If there are subjects with non-zero response scores, a combined skin (sum of dermal and superficial irritation) score, and a combined ocular (sum of conjunctiva and lacrimal) score at each time-point and for the sum across time points following product use (sum of Baseline (Visit 2) and Visit 3) will be determined and summarised using descriptive statistics.

For the secondary endpoints, each subject assessment (redness, dryness, burning, itching and stinging, as per Appendix 5) and combined score (summed across these 5 assessments)

 GlaxoSmithKline	Document Name	Clinical Protocol 207782		
	Type	Version	Document Identifier	Effective Date
	eldo_clinical_doc	2.0; Most-Recent; Effective; CURRENT	090032d580d48db0	26-May-2017 05:53:15
	Reason For Issue	Auto Issue		

will be similarly presented at each time point and for the sum across time points following product use (sum of Baseline (Visit 2) and Visit 3) for each of the test products.

Data will also be presented by sub-groups, contact lens wearer status (yes, no) and skin type (dry, normal/combined) at baseline.

No interim analyses are planned.

Adverse Events (AE) will be tabulated according to the current version of the Medical Dictionary for Regulatory Activities (MedDRA). Frequencies and percentages will be presented overall, for each system organ class, and for each preferred term for each of the test products. Summaries of treatment-emergent AE's, treatment-related AE's, and AE's leading to discontinuation, and serious AE's will be presented.

Detailed methodology for summary and statistical analyses of the data collected in this study will be documented in a Statistical Analysis Plan, which will be maintained and signed off prior to study unblinding.

 GlaxoSmithKline	Document Name	Clinical Protocol 207782		
	Type	Version	Document Identifier	Effective Date
	eldo_clinical_doc	2.0; Most-Recent; Effective; CURRENT	090032d580d48db0	26-May-2017 05:53:15
	Reason For Issue	Auto Issue		

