2. OBJECTIVE(S) AND ENDPOINT(S)

Objective(s)	Endpoint(s)
Primary	
Assessment of the cutaneous and ocular tolerance of two cosmetic facial cleansers after 21 (+ 2) days of product use per the intended instructions in healthy female subjects with clinically assessed sensitive skin.	Dermatologist and ophthalmologist visual assessment of cutaneous and ocular irritation after 21 (+ 2) days of test product use.
Secondary	
Assessment of the cutaneous and ocular tolerance of two cosmetic facial cleansers after 21 (+ 2) days of product use per the intended instructions in healthy female subjects with clinically assessed sensitive skin.	Subject self-assessment question responses (redness, dryness, burning, itching and stinging) with regards to product use experience on the face and around the eyes after 21 (+ 2) days of test product use.
To evaluate the general safety of two cosmetic facial cleansers.	Frequency and severity of Adverse Events

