9.3.4. Safety Analysis(es)

Adverse events will be tabulated according to the current version of the MedDRA. Frequencies and percentages will be presented overall, for each system organ class, and for each preferred term. Summaries of treatment-emergent AEs, treatment-related AEs, AEs leading to discontinuation, and serious AEs will be presented for each of the test products.

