**Table 1 Changes to Protocol Defined Analysis Plan**

Protocol	Statistical Analysis Plan	Rationale for Changes

 
Section 2 – Objectives and Endpoints
 
	
 
Section 1.2 Study Objectives.
 
 
The dermatologist and ophthalmologist visual assessment of cutaneous and ocular irritation objective/endpoint at Day 1 has been added as a secondary objective.
	
 
For clarification that the Day 21 is the primary endpoint of interest, whereas the Day 1 results are of secondary importance.
 

 
Section 9.2.3 - Criteria for Evaluation of Local Tolerance.
 
 
“This study will be considered a success if the majority (i.e. >50%) of subjects per treatment arm complete the study with combined dermatologist and ophthalmologist scores of zero at day 21 (+ 2).”
	
 
Section 4.4.1.1 - Primary efficacy endpoint definition.
 
 
Reference to subjects completing the study has been removed.
	
 
Requirement for subjects to complete the study is not applicable when assessing the success of the study. This was specified in error in the protocol. The analysis population definition has no requirement for subjects to complete the study for evaluability.
 

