## 6 Top-line Summary

The following outputs will be produced for the top-line report.

Table/Listing/Figure No.	Title
Table 14.1.1	Subject Disposition
Table 14.2.1.1	Frequency of Combined Dermatologist and Ophthalmologist Score – Intent To Treat Population
Table 14.3.1.1	Treatment Emergent Adverse Events by System Organ Class and Preferred Term – Safety Population
Table 14.2.3.1	Frequency of Combined Dermatologist Score – Intent To Treat Population
Table 14.2.4.1	Frequency of Combined Ophthalmological Score – Intent To Treat Population

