14.3.1.2	Treatment Emergent Adverse Events by System Organ Class, Preferred Term and Severity – Safety Population	Section 6
14.3.1.3	Treatment Emergent Treatment-Related Adverse Events by System Organ Class and Preferred Term – Safety Population	Table 14.3.1.1
14.3.1.4	Treatment Emergent Treatment-Related Adverse Events by System Organ Class, Preferred Term and Severity – Safety Population	Table 14.3.1.2

Listing No.	Listing Title (including population)	Template
14.3.2.1	Deaths – All Randomized Subjects	16.2.7.1
14.3.2.2	Serious Adverse Events leading to Discontinuation – All Randomized Subjects	16.2.7.1
16.1.7	Randomization information – All Randomized Subjects	Appendix 8
16.2.1.1	Subject Disposition – All Screened Subjects	Appendix 8
16.2.2	Individual Subjects Protocol Violation – All Randomized Subjects	Appendix 8
16.2.3.1	Exclusions from Analysis Populations – All Randomized Subjects	Appendix 8
16.2.4.1	Demographic Characteristics – All Randomized Subjects	Appendix 8
16.2.4.2	Medical History – All Randomized Subjects	Appendix 8
16.2.6.1	Dermatologist and Ophthalmologist Scores – All Randomized Subjects	Appendix 8
16.2.6.2.1	Subject Self-Assessment (Face) – All Randomized Subjects	Appendix 8
16.2.6.2.2	Subject Self-Assessment (Eye) – All Randomized Subjects	Appendix 8
16.2.7.1	All Adverse Events – All Randomized Subjects	Appendix 8
16.2.7.2	All Adverse Events – Non Randomized Subjects	16.2.7.1

Micellar Cleanser

207782

Draft Statistical Reporting and Analysis plan Amendment #1, 14 Aug 2017

---

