## 1 Introduction

This RAP addendum describes the changes, deviations and clarifications to the planned analysis described in the Statistical Reporting and Analysis Plan Amendment 1 and protocol version 2.0. These changes were identified during CSR development, and hence were identified after unblinding but prior to final CSR. These changes will be reflected in the final CSR.

The sections below provide the updated text that are required from the planned analysis, with section 5.0 providing further details on what was planned, the change and the reason for the change. A summary of the changes/clarifications are:

- Number of subjects who underwent the lactic acid sting test: this summary will be added to the disposition table 14.1.1.
- Safety population definition: The definition applied to the tables, figures and listings (TFLs) differed from the planned definition in the RAP amendment and protocol V2.0.
- Treatment emergent adverse event (TEAE) definition: No definition was previously provided; hence a definition has been added for clarity and consistency with the updated safety population definition.
- Update to study duration derivation in Listing 16.2.1.1

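### The SAP drops the by-product summary of serious adverse events that the protocol promises, and restricts its SAE listing to events that led to discontinuation

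*SAP*

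**What the plan says.** Protocol 9.3.4, after naming summaries of treatment-emergent and treatment-related events, continues: "AEs leading to discontinuation, and serious AEs will be presented for each of the test products". The Statistical Methods part of the protocol synopsis makes the same commitment: "Summaries of treatment-emergent AE's, treatment-related AE's, and AE's leading to discontinuation, and serious AE's will be presented". The objectives table in Protocol 2 includes as a secondary objective: "To evaluate the general safety of two cosmetic facial cleansers".

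SAP 4.6.1 describes four AE tables: 14.3.1.1 (TEAEs), 14.3.1.2 (TEAEs by severity), 14.3.1.3 (treatment-related TEAEs) and 14.3.1.4 (treatment-related TEAEs by severity). It then provides for a deaths listing (14.3.2.1) and states: "Serious adverse events leading to discontinuation will be listed". The SAP 7 list of displays gives Listing 14.3.2.2 the same scope in its title: "Serious Adverse Events leading to Discontinuation". All AEs go into Listings 16.2.7.1 (randomised subjects) and 16.2.7.2 (non-randomised subjects). The single AE output in the SAP 6 top-line set is Table 14.3.1.1, "Treatment Emergent Adverse Events by System Organ Class and Preferred Term".

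The Addendum rewrites 4.6.1 to define TEAEs. It repeats the sentence on serious events unchanged and adds no SAE summary.

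**The concern.** The protocol promises a summary of serious AEs and a summary of AEs leading to discontinuation. The SAP has a table for neither, and its one SAE listing covers the overlap of the two categories instead of each in full. A programmer who follows the SAP exactly will produce no count of subjects with serious events in each product group and no complete SAE listing.

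What is at stake is the reporting of the general-safety objective. Listing 14.3.2.2 could be empty although non-fatal serious events had occurred, and no other planned display would give the serious-event count. The departure is also undeclared, so someone comparing report with protocol would find no explanation for it.

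**Working it through.** There is no plan figure to reproduce. The check sets the protocol's commitments against the SAP's displays.

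**Step 1. Promised summaries (Protocol 9.3.4) against planned tables (SAP 4.6.1 and SAP 7).**

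| Promised summary, by product | SAP table |
|---|---|
| Treatment-emergent AEs | 14.3.1.1, 14.3.1.2 |
| Treatment-related AEs | 14.3.1.3, 14.3.1.4 |
| AEs leading to discontinuation | none |
| Serious AEs | none |

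Promised summaries with an AE table: 2 of 4. AE tables for serious events: 0 of 4. The general sentence in SAP 4.6.1 about summarising all AEs by system organ class and preferred term does not separate serious events, so it does not fill the gap.

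**Step 2. Where each kind of event appears.**

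| Event | Dedicated display | Elsewhere |
|---|---|---|
| Fatal | Listing 14.3.2.1 | TEAE tables, all-AE listing |
| Serious, led to discontinuation | Listing 14.3.2.2 | TEAE tables, all-AE listing |
| Serious, non-fatal, no discontinuation | none | TEAE tables, all-AE listing, not separated as serious |
| Non-serious, led to discontinuation | none | TEAE tables, all-AE listing (withdrawal column), Table 14.1.1 counts of AE as primary reason |

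Entries for the TEAE tables assume a treatment-emergent event in a treated subject. The third row is the main gap. The fourth is partly covered, but Table 14.1.1 gives only a primary reason by product, with no event term.

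**Step 3. Was the change declared?** SAP 5 says that changes from the protocol analysis are set out in its Table 1, which has 2 entries: the added Day 1 objective, and the revised success criterion ("Reference to subjects completing the study has been removed"). The Addendum's introduction has 4: the sting-test count, the Safety population, the TEAE definition, and "Update to study duration derivation in Listing 16.2.1.1". Total 2 + 4 = 6, and 0 of 6 concern SAE or discontinuation outputs.

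**Step 4. Scale.** One affected subject is 1/46 = 2.2% of a planned arm, or 1/40 = 2.5% of the minimum number of completers per arm. This shows only what one subject weighs. The documents do not allow an expected number of SAEs to be derived.

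**Step 5. Could serious events be identified from the all-AE listing?** The Listing 16.2.7.1 shell as extracted shows intensity, relatedness, action taken and withdrawal, but no seriousness column. This is weak evidence. The same shell has a footnote 4 with no matching marker in the header. The Listing 16.2.6.1 footnotes define a combined score that has no column in the extracted header. The Deaths listing reuses the 16.2.7.1 shell although it needs a cause of death, so shells are evidently adapted. The conclusion does not depend on this step.

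**The case against.** The strongest reply is that nothing is lost. A treatment-emergent serious event in a treated subject is counted by product in Table 14.3.1.1 and by severity in 14.3.1.2. Every AE is listed, and deaths have their own listing. That stands, and it limits the finding: what is missing is the separate count and the complete listing, not the data.

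Second, the title of Listing 14.3.2.2 states its restriction, so a careful reader would not take an empty listing to mean that no SAEs occurred. This is fair and weakens any claim that the report would mislead. It does not help the reader who wants the number of serious events, because no other display gives it.

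Third, serious events may be few or absent among healthy women using a cosmetic cleanser for about three weeks. That is plausible, but the documents cannot settle it, and the protocol's promise does not depend on event frequency.

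Fourth, the restricted wording may be a slip for a listing of SAEs together with AEs leading to discontinuation. That is possible, but the SAP text, the list of displays and the Addendum all carry it. A slip repeated three times still needs correcting, and the missing tables would remain.

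Fifth, the protocol does not promise an SAE output in the top-line set, nor a system organ class and preferred term layout for these two summaries. Both points are right, and neither is held against the plan here.

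**Conclusion.** The concern holds. The SAP omits the by-product summary of serious AEs promised in Protocol 9.3.4, limits its one SAE listing besides deaths to events that led to discontinuation, and declares neither. The promised summary of AEs leading to discontinuation is also missing as an AE display, with partial cover from the disposition table and the all-AE listing.

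This is more than missing detail, because the SAP states a narrower rule than the protocol does. It should be fixed, but its weight is limited: no data are lost, the primary endpoint and success rule are unaffected, and the number of events concerned is unknown and may be zero. The conclusion rests on reading the SAP's list of displays as complete. The SAP supports that reading, since it gives its purpose as describing the planned analyses and outputs for the study report.

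**What to change.** - Replace Listing 14.3.2.2 with two listings: all SAEs, and all AEs leading to discontinuation whether serious or not.
- Add two by-product tables: serious TEAEs, and TEAEs leading to discontinuation. The layout of Table 14.3.1.1 is a sensible model, though the protocol does not prescribe it.
- Confirm that the shell for Listings 16.2.7.1 and 16.2.7.2 has a seriousness column, or add one. In 16.2.7.2 it would also mark SAEs in subjects never randomised, which is useful because Protocol 4.3 asks for SAE information on screen failures.
- If the restriction is intended, state it with a rationale in the change table instead.

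The cost is SAP wording and minor programming. No new data collection should be needed: Protocol 7.2 has AE and SAE information recorded in the CRF, the SAE form in Protocol 7.4 requires the seriousness criterion, and Listing 14.3.2.2 cannot be produced without a seriousness flag. That a usable flag is in the database is an inference from these points and should be confirmed. The Addendum was written after unblinding, while the study report was being developed, so displays added at that stage or later must be declared as post-unblinding changes. Because they restore what the protocol already specified, that is easy to justify.

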## 4.7 Analysis of Other Variables

Not applicable.

## 5 Changes to the Protocol Defined Statistical Analysis Plan

Any changes from the originally planned statistical analysis specified in the protocol (dated 26-May-2017) are outlined in Table 1.

[figure not shown]
**Table 1 Changes to Protocol Defined Analysis Plan**

Protocol	Statistical Analysis Plan	Rationale for Changes

 
Section 2 – Objectives and Endpoints
 
	
 
Section 1.2 Study Objectives.
 
 
The dermatologist and ophthalmologist visual assessment of cutaneous and ocular irritation objective/endpoint at Day 1 has been added as a secondary objective.
	
 
For clarification that the Day 21 is the primary endpoint of interest, whereas the Day 1 results are of secondary importance.
 

 
Section 9.2.3 - Criteria for Evaluation of Local Tolerance.
 
 
“This study will be considered a success if the majority (i.e. >50%) of subjects per treatment arm complete the study with combined dermatologist and ophthalmologist scores of zero at day 21 (+ 2).”
	
 
Section 4.4.1.1 - Primary efficacy endpoint definition.
 
 
Reference to subjects completing the study has been removed.
	
 
Requirement for subjects to complete the study is not applicable when assessing the success of the study. This was specified in error in the protocol. The analysis population definition has no requirement for subjects to complete the study for evaluability.
 

## 6 Top-line Summary

The following outputs will be produced for the top-line report.

Table/Listing/Figure No.	Title
Table 14.1.1	Subject Disposition
Table 14.2.1.1	Frequency of Combined Dermatologist and Ophthalmologist Score – Intent To Treat Population
Table 14.3.1.1	Treatment Emergent Adverse Events by System Organ Class and Preferred Term – Safety Population
Table 14.2.3.1	Frequency of Combined Dermatologist Score – Intent To Treat Population
Table 14.2.4.1	Frequency of Combined Ophthalmological Score – Intent To Treat Population

**Attachment 1: List of Data Displays****7 List of Tables, Figures and Listings**

In all outputs, the treatment labels and order for presentation in tables and listings is:

- 1) Micellar Cleanser
- 2) Micellar Foaming Cleanser

Table No.	Table Title (including population)	Template
14.1.1	Subject Disposition	Section 6
14.1.2.1	Demographic Characteristics – Safety Population	Section 6
14.1.2.2	Demographic Characteristics – Intent To Treat Population	Table 14.1.2.1
14.2.1.1	Frequency of Combined Dermatologist and Ophthalmologist Score – Intent To Treat Population	Section 6
14.2.1.2	Frequency of Combined Dermatologist and Ophthalmologist Score by Strata – Intent To Treat Population	Table 14.2.1.1
14.2.2.1	Frequency of Combined Dermatologist and Ophthalmologist Score (Modified) – Intent To Treat Population	Table 14.2.1.1
14.2.2.2	Frequency of Combined Dermatologist and Ophthalmologist Score (Modified) by Strata – Intent To Treat Population	Table 14.2.1.1
14.2.3.1	Frequency of Combined Dermatologist Score – Intent To Treat Population	Table 14.2.1.1

14.2.3.2	Frequency of Combined Dermatologist Score by Strata – Intent To Treat Population	Table 14.2.1.1
14.2.4.1	Frequency of Combined Ophthalmological Score – Intent To Treat Population	Table 14.2.1.1
14.2.4.2	Frequency of Combined Ophthalmological Score by Strata – Intent To Treat Population	Table 14.2.1.1
14.2.5.1	Frequency of Dermal Response Score – Intent To Treat Population	Section 6
14.2.5.2	Frequency of Dermal Response Score by Strata – Intent To Treat Population	Table 14.2.5.1
14.2.6.1	Frequency of Conjunctiva Involvement Score – Intent To Treat Population	Section 6
14.2.6.2	Frequency of Conjunctiva Involvement Score by Strata – Intent To Treat Population	Table 14.2.6.1
14.2.7.1	Frequency of Lacrimal Intensity Score – Intent To Treat Population	Table 14.2.5.1
14.2.7.2	Frequency of Lacrimal Intensity Score by Strata – Intent To Treat Population	Table 14.2.5.1
14.2.8.1	Frequency of Subject Assessment Scores for Eyes - Intent to Treat Population	Section 6
14.2.8.2	Frequency of Subject Assessment Combined Score for Eyes - Intent to Treat Population	Section 6
14.2.9.1	Frequency of Subject Assessment Scores for Face - Intent to Treat Population	Table 14.2.8.1
14.2.9.2	Frequency of Subject Assessment Combined Score for Face - Intent to Treat Population	Table 14.2.8.2
14.3.1.1	Treatment Emergent Adverse Events by System Organ Class and Preferred Term – Safety Population	Section 6

14.3.1.2	Treatment Emergent Adverse Events by System Organ Class, Preferred Term and Severity – Safety Population	Section 6
14.3.1.3	Treatment Emergent Treatment-Related Adverse Events by System Organ Class and Preferred Term – Safety Population	Table 14.3.1.1
14.3.1.4	Treatment Emergent Treatment-Related Adverse Events by System Organ Class, Preferred Term and Severity – Safety Population	Table 14.3.1.2

Listing No.	Listing Title (including population)	Template
14.3.2.1	Deaths – All Randomized Subjects	16.2.7.1
14.3.2.2	Serious Adverse Events leading to Discontinuation – All Randomized Subjects	16.2.7.1
16.1.7	Randomization information – All Randomized Subjects	Appendix 8
16.2.1.1	Subject Disposition – All Screened Subjects	Appendix 8
16.2.2	Individual Subjects Protocol Violation – All Randomized Subjects	Appendix 8
16.2.3.1	Exclusions from Analysis Populations – All Randomized Subjects	Appendix 8
16.2.4.1	Demographic Characteristics – All Randomized Subjects	Appendix 8
16.2.4.2	Medical History – All Randomized Subjects	Appendix 8
16.2.6.1	Dermatologist and Ophthalmologist Scores – All Randomized Subjects	Appendix 8
16.2.6.2.1	Subject Self-Assessment (Face) – All Randomized Subjects	Appendix 8
16.2.6.2.2	Subject Self-Assessment (Eye) – All Randomized Subjects	Appendix 8
16.2.7.1	All Adverse Events – All Randomized Subjects	Appendix 8
16.2.7.2	All Adverse Events – Non Randomized Subjects	16.2.7.1

Micellar Cleanser

207782

Draft Statistical Reporting and Analysis plan Amendment #1, 14 Aug 2017

---

## 8 Template for Tables, Figures and Listings

Protocol: 207782

Program Run Date: ddmonyyyy

Table 14.1.1  
Subject Disposition

	Micellar Cleanser N (%)	Micellar Foaming Cleanser N (%)	Overall N (%)
TOTAL SUBJECTS SCREENED			XX
SUBJECTS NOT RANDOMISED			XX
DID NOT MEET STUDY CRITERIA			XX (XX.XX)
ADVERSE EVENT			XX (XX.XX)
LOST TO FOLLOW - UP			XX (XX.XX)
PROTOCOL VIOLATION			XX (XX.XX)
WITHDRAWAL OF CONSENT			XX (XX.XX)
OTHER			XX (XX.XX)
SUBJECTS RANDOMISED	XX	XX	XX
COMPLETED STUDY	XX (XX.XX)	XX (XX.XX)	XX (XX.XX)
DID NOT COMPLETE STUDY	XX (XX.XX)	XX (XX.XX)	XX (XX.XX)
DID NOT MEET STUDY CRITERIA	XX (XX.XX)	XX (XX.XX)	XX (XX.XX)
ADVERSE EVENT	XX (XX.XX)	XX (XX.XX)	XX (XX.XX)
LOST TO FOLLOW - UP	XX (XX.XX)	XX (XX.XX)	XX (XX.XX)
PROTOCOL VIOLATION	XX (XX.XX)	XX (XX.XX)	XX (XX.XX)
WITHDRAWAL OF CONSENT	XX (XX.XX)	XX (XX.XX)	XX (XX.XX)
OTHER	XX (XX.XX)	XX (XX.XX)	XX (XX.XX)
SAFETY POPULATION	XX (XX.XX)	XX (XX.XX)	XX (XX.XX)
ITT POPULATION	XX (XX.XX)	XX (XX.XX)	XX (XX.XX)
PP POPULATION	XX (XX.XX)	XX (XX.XX)	XX (XX.XX)

PPD

Page X of Y

**Programming note:** For categories under 'Subjects Not Randomised' percentages will be calculated using the number of 'All Screened Subjects' as the denominator. Percentages under the 'Subjects Randomised' categories will be computed using number of subjects randomised as the denominator.

Micellar Cleanser

207782

Draft Statistical Reporting and Analysis plan Amendment #1, 14 Aug 2017

---

Protocol: 207782

Program Run Date: ddmonyyyy

Table 14.1.2  
Demographic Characteristics  
Safety Population

Study Population: Safety (N=xxx)

